## **8. Informed Consent Process:**

IRB approval will be obtained prior to patient recruitment. Patients will be identified as they present to the orthopaedic pediatric service of Arnold Palmer Hospital / Orlando Health Inc. with a qualifying injury to determine their interest in participating in the study. The study will be explained to them, they will have an opportunity to read the consent, have their questions answered. If they agree to participate, they will be randomized to a treatment arm as described above.

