Randomization to form the two trial groups will be performed by utilizing the computer program 'Research Randomizer' to create the randomization list. Randomization will be 50/50 or 1 to 1. The assignments will be printed out and placed into numbered envelopes.

The envelopes will be kept in a box in the [name] office. Group 1 will receive 0.25 mL of 1% buffered lidocaine delivered by the J-tip injector. Group 2 will be formed by subjects receiving 1.5 mL of 1% plain lidocaine injected by syringe and 25 gauge needle. The site of administration for this trial will be standard femoral and/or sciatic nerve block locations. The regional block will be performed under ultrasound guidance and with the assistance of nerve stimulation. General anesthesia will be given when the patient is in the operating room. This is done after the regional blocks have already been completed.

Administration of sedative and anxiolytic medications before or during the regional nerve block procedures will be based on nervous and pain VAS scores and anesthesiologist graded anxiety scores. If anxiety levels are indicated to be less than four, no sedation will be administered prior to the nerve block procedure. If anxiety scores are four to seven, then two mg to a maximum of four mg of Versed IV will be administered just prior to the local anesthesia administration. If anxiety scores are greater than seven, then two mg to a maximum of four mg of IV Versed will be administered just prior to the local anesthesia administration. If anesthesiologist observed anxiety levels remain above 7, then 20 mcg to a max of 40 mcg of IV Precedex will subsequently be administered.

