The current observations of clinical efficacy in the delivery of local anesthesia by either needle or J-tip introduction have shown that the superficial and subcutaneous tissues are adequately anesthetized. Pain is usually encountered as the touhy needle, nerve block needle, penetrates the fascia of the muscle. The fascia is a barrier to the deeper tissues and is not anesthetized with any local anesthetic. Additional medications may be administered during the needle insertion through the fascia during the regional block. If pain VAS is greater than four, and IV Versed was not administered due to anxiety scores between four and seven, then two mg to a maximum of four mg of IV Versed will be administered. If pain continues to be above four and IV Precedex was not administered due to anxiety levels greater than seven, then 20 mcg to a max of 40 mcg IV Precedex will be administered. If pain continues to be greater than four, then 25 mcg Fentanyl to a maximum of 50 mcg will be administered. If pain values continue to be above seven, then 100 mg of IV propofol will be given. No matter what amount and type of sedative or anxiolytic is administered during the nerve block procedure, the first VAS measure at each time point will be the one of record for analysis in this study.

Patients will indicate their level of nervousness by completing a visual analogue scale, after admission to the preoperative area, for how nervous they are prior to their procedure. The anesthesiologist through observational measurement on a scale of 0-10 will also measure patient anxiety levels. A level of ten will be the highest observed measure of anxiety. These scores will assist in identifying patients that may need more general types of anesthesia prior to the nerve block. This will also allow for further evaluation of limitations due to the amount of pre-op anesthesia of patients in the study.

Femoral nerve blocks will be performed on all arthroscopic procedures. Single injection sciatic nerve blocks will be utilized in addition to femoral catheter nerve blocks for patients undergoing arthroscopic surgery with ACL reconstruction or if lateral meniscus repair is expected to be performed. The site or sites of injection on the operative lower extremity will be chosen, a timeout taken and sterile preparation performed by the

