## **5. Study Population:**

The 15 patients enrolled to account for withdrawals will cover patients who wish to self-select to the J-tip or needle group and do not wish to be randomized. These patients will not be in the final analysis. Patients who wish to switch groups after being randomized will be allowed to switch, but will be withdrawn from final analysis. If a patient does not wish to have either method of local anesthesia delivery prior to the regional block, they will be withdrawn from final analysis.

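### Nothing in the plan withholds the assigned arm from the child or the anesthesiologist until nervousness, anxiety, baseline pain and the first sedation decision are recorded

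*Combined protocol and SAP*

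**What the plan says.** **Approach and randomisation.** Section 8 describes recruitment: "Patients will be identified as they present to the orthopaedic pediatric service". It then says: "If they agree to participate, they will be randomized to a treatment arm as described above". Section 4 gives the allocation as "Randomization will be 50/50 or 1 to 1" and the mechanism as "The assignments will be printed out and placed into numbered envelopes". The envelopes are kept in an office. The text does not say that they are sealed or opaque, who opens them, or when.

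**Scores before the injection.** Section 4 says: "Patients will indicate their level of nervousness by completing a visual analogue scale, after admission to the preoperative area". On the second score it says: "The anesthesiologist through observational measurement on a scale of 0-10 will also measure patient anxiety levels". A pain VAS is also completed before each local anesthetic injection.

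**Use of the scores.** Section 4 says: "Administration of sedative and anxiolytic medications before or during the regional nerve block procedures will be based on nervous and pain VAS scores". The anesthesiologist's anxiety grade is a further input. Sedation set by the anxiety bands is given immediately before the local anesthetic, with amounts stated as ranges. One anesthesiologist performs every local injection and every block.

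**Knowledge of the arm.** Section 5 says: "Patients who wish to switch groups after being randomized will be allowed to switch, but will be withdrawn from final analysis". A patient who wants neither method is also withdrawn from the analysis. No blinding of the child, the anxiety grader or the sedation decision is described.

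**The concern.** A child who expects a needle may report more nervousness than one who expects a needleless device. An anesthesiologist who knows the arm may grade the same behaviour differently. Both scores feed the sedation given just before the randomised injection, so knowledge of the arm could change how much sedation each group receives before its pain is measured.

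If the needle arm were sedated more, its reported pain would most plausibly fall. That would shrink any J-Tip advantage both at the local injection and at the block, and pain from the block is the primary objective. The nervous VAS and the pre-injection pain VAS would also stop being true baselines, since they would be measured after a possible effect of assignment.

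The protocol takes care over other influences on pain report: parents are out of the room, and music and screens are off. This route is left open.

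**Working it through.** The point rests on the order of events, so I set the steps side by side and then asked how much the reported balance can exclude.

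**1. Order of events**

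| Step | Source | Is the arm withheld? |
|---|---|---|
| Identified on the orthopaedic service, consent, randomised | Section 8 | Not stated |
| Nervous VAS after preoperative admission | Section 4 | Not stated |
| Anesthesiologist's 0-10 anxiety grade | Section 4 | Not stated |
| Pain VAS before the local injection | Section 4 | Not stated |
| Sedation under the anxiety bands, just before the local injection | Section 4 | Not stated |
| Local injection by the assigned device | Section 4 | Impossible from here on |

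The order of the pre-injection pain VAS relative to pre-injection sedation is not given. The switch rule shows that the arm can be known between randomisation and treatment, but not at which of these steps.

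**2. What the Results report.** The opening paragraph of the regression part lists variables without a significant difference between arms. They include the types of first, second and third sedation, the three total quantities, and the pain VAS before the femoral and sciatic local injections. The nervous VAS and the anesthesiologist's anxiety grade are not listed. The two regressions (Tables 4 and 9) adjust for age, gender, ethnicity, BMI and thigh circumference, and not for sedation or any baseline score.

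**3. What non-significance can exclude.** Inputs: 54 needle and 57 J-Tip patients (Table 1), assumed to apply to these comparisons too. Two-sided alpha 0.05 is assumed because the plan states none.

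- Standard error of a standardised difference: sqrt(1/54 + 1/57) = 0.190.
- Difference detectable with 80% power: (1.960 + 0.842) × 0.190 = 0.53 SD. At the planned 50 per group it is 2.802 × sqrt(2/50) = 0.56 SD.
- Power at a true difference d: Phi(d/0.190 − 1.960). This gives 18% for 0.2 SD, 35% for 0.3 SD and 75% for 0.5 SD.
- For a yes/no sedation rate (assumed rates, two-proportion normal approximation), power is 18% for 50% against 60%, and 58% for 50% against 70%.

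**4. Illustration of possible size.** The documents give no nervous VAS distribution and no effect of knowing the arm, so every input here is assumed: a normal score with SD 2 to 3, a rise of 0.5 to 1.0 points in the needle arm, and the nervous VAS alone as trigger at the lower sedation threshold of 4. The extra share crossing is Phi((mean + rise − 4)/SD) − Phi((mean − 4)/SD).

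| Assumed mean | Rise 0.5, SD 3 | Rise 0.5, SD 2 | Rise 1.0, SD 3 | Rise 1.0, SD 2 |
|---|---|---|---|---|
| 4 (at the threshold) | 6.6% | 9.9% | 13.1% | 19.1% |
| 7 | 3.7% | 2.7% | 6.7% | 4.4% |

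The range is thus about 7% to 19% with the mean at the threshold, which is close to the worst case, and about 3% to 7% with a mean of 7.

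**The case against.** The strongest reply is that early disclosure is inferred. Section 8 says that consenting patients are randomised, but gives no time and does not say that the arm is revealed then. The switch rule fits equally well with a reveal at the bedside when the device is produced. This stands: the documents do not establish that the child or the anesthesiologist knew the arm when the scores were taken. What remains is that nothing prevents it.

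Second, the reported balance is reassuring. A reader might infer that it covers only nominal sedation codes and can be set aside. It cannot: sedation amounts and pre-injection pain VAS were compared too, and none differed significantly. This lowers concern about the observed data. It does not close the question, because the two scores most exposed to knowledge of the arm are missing and power for a moderate imbalance is low.

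Third, there are partial safeguards. Sedation follows score bands, and patients graded below the lowest band receive none before the block, so it would be wrong to say that sedation precedes every VAS. The first VAS at each time point is the one of record, which limits the effect of later sedation. Neither feature protects against sedation given before the injection, because the triggering scores are subjective and the amounts are ranges. Section 7 allows regression adjustment, but scores or sedation recorded after the arm is known are post-randomisation variables, so adjusting for them is not a clean remedy.

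Fourth, opening the envelope after sedation would first present the arm, and the option to switch or decline, to a sedated minor. That is a sound objection to a simple delay, and it fixes where the opening must fall.

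**Conclusion.** The design point holds. Followed as written, the plan leaves the nervous VAS, the anxiety grade, the baseline pain VAS and pre-injection sedation open to knowledge of the arm, and this could bias the local and block pain comparisons. It should be corrected.

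The size of any bias is not known. The 3% to 19% span of extra threshold crossings rests wholly on assumed inputs and is an illustration, not an estimate. The firmer figure is that the reported comparisons had 80% power only for differences of about 0.53 SD, given 54 and 57 patients and two-sided alpha 0.05.

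Two stronger readings are tempting. One is that the non-significant block-pain result in the Results was produced by heavier sedation of the needle arm. Such a null lies in the direction this weakness could produce, but nothing in the documents shows that it did, and the reported sedation comparisons give no sign of it. The other is that early disclosure caused switch requests and so removed randomised patients from the analysis. The documents give neither the time of disclosure nor a count of switches.

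**What to change.** Add to Section 4, and align Section 8 with it: assignments are held in sealed, opaque, numbered envelopes. The envelope is opened only after the nervous VAS, the anesthesiologist's anxiety grade, the baseline pain VAS and the initial sedation decision under the existing rules (including the amount chosen within the stated range) have been recorded, and before any sedative is given. State who opens it, record the time, and state who is told. Opening before sedation means that the Section 5 option to switch or decline is not first offered to a sedated child.

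The attached results cannot benefit from a changed sequence. For them, report by arm the nervous VAS, the anxiety grade and the sedation received (number and percentage for types, a distribution for amounts), with confidence intervals for the differences. State when and to whom the arm was revealed.

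**Cost.** A few sentences of protocol text, one recorded time per patient, and both devices at hand when the envelope is opened. Protection is partial: the arm is known for any later sedation step, for sedation during the block, and for the second (sciatic) site, including its baseline VAS. The sedation rules themselves do not change.

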## **9. Privacy and Confidentiality:**

Any PHI will be kept on a password protected database and will be linked only with a study identification number for this research. All data will be entered into a computer that is password protected. Data will be stored in a locked office of the investigators and maintained for a minimum of five years after the completion of the study.

## **10. Risk/Benefit:**

### **10.1 Possible Risk to participants:**

- Allergic reaction to lidocaine with a previously unknown allergy.
- Blood reflux at injection point.
- Skin wheal.
- Skin bruising.

### **10.2 Possible Benefits to Participants**

- Decreased pain from local anesthesia infiltration compared to needle injected local anesthetic at nerve block site.
- Decreased pain during femoral and/or sciatic nerve block procedure.
- Possible increased efficacy of femoral nerve block leading to decreased post-operative pain, medication use and pharmacologic side effects.

## **11. Data Safety Monitoring:**

Monitoring is an ongoing review of the study throughout its duration. Safeguards to protect research participant data and identity include but are not limited to restricting access to data to the principal, sub investigators and the study coordinators. Identifiable PHI will not be used in any manuscript and any data containing PHI will be stored in a password protected computer.

## **12. Conflict of Interest:**

This is not a sponsored study. There is no additional benefit to the investigator(s) beyond academic publication or presentation. No direct financial support for the study will be provided from any entity. No royalties will be received from any implants implanted at Orlando Health.

## **13. Publication and Presentation Plans:**

This project will be presented at Orthopaedic meetings and the manuscript is to be presented for publication in a peer reviewed Orthopaedic journal.

## **15. Appendices :**

“Nervous” Visual Analogue Scale (VAS)

Pain Visual Analogue Scale (VAS)

Arthroscopic Surgery Satisfaction Questionnaire Parent (J-Tip)

Arthroscopic Surgery Satisfaction Questionnaire Child (J-Tip)

Arthroscopic Surgery Satisfaction Questionnaire Parent (Needle)  
Arthroscopic Surgery Satisfaction Questionnaire Child (Needle)  
Home medication logs

## Results:

### Descriptive Statistics: Visual Analogy Scores (VAS) After Local Femoral and Local Sciatic Nerve Blocks

As seen in Table 1, the mean VAS immediately after local femoral for is 1.54 with a standard deviation 1.524 and the mean VAS immediately after local femoral for Needle Injections is 3.57 with a standard deviation 2.133. The mean VAS immediately after local femoral for J-Tip injections is 2.03 less than the mean VAS immediately after local femoral for Needle Injections. The difference time shows a large time gap and variation between the two injection types.

As seen in Table 1, the mean VAS immediately after local sciatic for is 2.272 with a standard deviation 2.1631 and the mean VAS immediately after local sciatic for Needle Injections is 4.5 with a standard deviation 2.4553. The mean VAS immediately after local sciatic for J-Tip injections is 2.228 less than the mean VAS immediately after local sciatic for Needle Injections. The difference time shows a large time gap and variation between the two injection types.

	Injection Type	N	Mean	Standard Deviation	Standard Error Mean
VAS Immediately After Local Femoral	Needle	54	3.57	2.133	.290
	J-Tip	57	1.54	1.524	.202
VAS Immediately After Local Sciatic	Needle	54	4.500	2.4553	.3341
	J-Tip	57	2.272	2.1631	.2865

Table 1: Group Statistics

### Two-Sample T Test: Visual Analogy Scores (VAS) After Local Femoral and Local Sciatic Nerve Blocks

#### VAS Immediately After Local Femoral:

$H_0$  : No statistically significant difference exists between the mean of the VAS Immediately After Local Femoral for Needle Injections and the mean of VAS Immediately After Local Femoral in the J-Tip Injections.

$H_a$ : A statistically significant difference exists between the mean of the VAS Immediately After Local Femoral for Needle Injections and the mean of VAS Immediately After Local Femoral in the J-Tip Injections.

The VAS Immediately After Local Femoral for J-Tip Injections exceeds the mean VAS Immediately After Local Femoral for Needle Injections to a statistically significant degree,  $t(95.525) = 5.792$ ,  $p < .01$ , CI [1.328, 2.732], as indicated within Table 2.

VAS Immediately After Local Sciatic:

$H_0$  : No statistically significant difference exists between the mean of the VAS Immediately After Local Sciatic for Needle Injections and the mean of VAS Immediately After Local Sciatic in the J-Tip Injections.

$H_a$ : A statistically significant difference exists between the mean of the VAS Immediately After Local Sciatic for Needle Injections and the mean of VAS Immediately After Local Sciatic in the J-Tip Injections.

The VAS Immediately After Local Sciatic for J-Tip Injections exceeds the mean VAS Immediately After Local Sciatic for Needle Injections to a statistically significant degree,  $t(109) = 5.080$ ,  $p < .01$ ,  $[1.3587, 3.0974]$ , as indicated within Table 2.

		T-Test For Equality of Means							95% Confidence Interval of the Difference	
		F	Significance	t	df	Significance (2-tailed)	Mean Difference	Standard Error Difference		
VAS Immediately After Local Femoral	Equal Variances Assumed	4.491	.036	5.792	109	.000	2.030	.351	1.336	2.725
	Equal Variances Not Assumed			5.741	95.525	.000	2.030	.354	1.328	2.732
VAS Immediately After Local	Equal Variances Assumed	.515	.474	5.080	109	.000	2.2281	.4386	1.3587	3.0974

Sciatic	Equal Variances Not Assumed			5.062	105.576	.000	2.2281	.4401	1.3554	3.1007
---------	--	--	--	-------	---------	------	--------	-------	--------	--------

Table 2: Independent Samples Test

Ordinary Least Squares Regression: Visual Analogy Scores (VAS) After Local Femoral and Local Sciatic Nerve Blocks

No statistical significance when comparing means Injection Type the following variables: 1st Type of Sedation, 1st Total Quantity of sedation used (mg), 2nd Type of Sedation Used, Total Quantity 2nd Type of sedation used (mcg), 3rd Type of Sedation Used, Total Quantity 3rd Type of sedation used (mcg), Visual Analog Scale (VAS) prior to local femoral, VAS prior to femoral, VAS immediately after femoral, VAS prior to local sciatic, VAS prior to sciatic, VAS immediately after sciatic, VAS prior to PACU Discharge.

VAS Immediately After Local Femoral:

Ordinary Least Squares Regression is utilized to determine if the Visual Analog Scale (VAS) immediately after local femoral for Needle Injections is significantly different from J-Tip Injections. This regression is run to determine if the injection type can statistically predict VAS immediately after local femoral. There is an independence of residuals, as assessed by a Durbin-Watson statistic, of 1.688 (Table 4). The assumptions of linearity, independence of errors, homoscedasticity, unusual points, and normality of residuals were met. The model is statistically significant,  $F (6, 100) = 10.215, p \leq .001$ , adj.  $R^2 = .343$ . Injection type statistically significantly predicts VAS immediately after local femoral, as seen in Table 3,  $\beta = -2.020, t = -6.266, p \leq .001$ . The beta explains that if a J-tip injection was given it would decrease the VAS immediately after local femoral by approximately 2. Regression coefficients and standard errors can be found in Appendix.

Variable	Adjusted R 	Model			Injection Type		
		df	F	Sig.	Beta	T	Sig.
VAS Immediately After Local Femoral	.343	6	10.215	.000	-2.020	-6.266	.000

Table 3: Beta Explanation for VAS Immediately After Local Femoral

Model	R	R 	Adjusted R 	Standard Error of the Estimate	Durbin-Watson
1	.616 a	.380	.343	1.656	1.688

- Predictors: (Constant), Thigh Circumference (cm), Ethnicity, Injection Type, Age, Gender BMI
- Dependent Variable: VAS Immediately After Local Femoral

Table 4: Model Summary

Model		Sum of Squares	df	Mean Square	F	Sig.
1	Regression	168.140	6	28.023	10.215	.000 b
	Residual	274.327	100	2.743		
	Total	442.467	106			

a. Dependent Variable: VAS Immediately After Local Femoral  
b. Predictors: (Constant), Thigh Circumference (cm), Ethnicity, Injection Type, Age, Gender BMI

Table 5: ANOVAa

		Unstandardized Coefficients		Standardized Coefficients				95% Confidence Interval for B	
Model		B	Std. Error	Beta	t	Sig.	Lower Bound	Upper Bound	
1	(Constant)	9.774	2.119		4.613	.000	5.570	13.977	
	Injection Type	-2.020	.322	-.496	-6.266	.000	-2.660	-1.381	
	Gender	.504	.340	.124	1.481	.142	-.171	1.179	
	Age	-.250	.105	-.193	-2.367	.020	-.459	-.040	
	Ethnicity	-.021	.117	-.014	-.177	.860	-.253	.212	
	BMI	-.079	.065	-.186	-1.225	.223	-.208	.049	
	Thigh Circumference (cm)	-.021	.038	-.083	-.545	.587	-.097	.055	

a. Dependent Variable: VAS Immediately After Local Femoral

Table 7: Coefficientsa

VAS immediately after local sciatic:

Ordinary Least Squares Regression is utilized to determine if the Visual Analog Scale (VAS) immediately after local sciatic for Needle Injections is significantly different from J-Tip Injections. This regression is run to determine if the injection type can statistically predict VAS immediately after local sciatic. There is an independence of residuals, as assessed by a Durbin-Watson statistic, of 1.798 (Table 9). The assumptions of linearity, independence of errors, homoscedasticity, unusual points, and normality of residuals were met. The model is statistically significant,  $F(6, 100) = 6.178$ ,  $p \leq .001$ , adj.  $R^2 = .227$ . Injection type statistically significantly predicts VAS immediately after local sciatic, as seen in Table 8  $\beta = -2.248$ ,  $t = -5.191$ ,  $p \leq .001$ . The beta explains that if a J-tip injection was given it would decrease the VAS immediately after local sciatic by approximately 2. Regression coefficients and standard errors can be found in Appendix.

Variable	Adjusted R 	Model			Injection Type		
		df	F	Sig.	Beta	T	Sig.
VAS Immediately After Local Sciatic	.277	6	6.178	.000	-2.248	-5.191	.000

Table 8: Beta Explanation for VAS Immediately After Local Sciatic

Model	R	R 	Adjusted R 	Standard Error of the Estimate	Durbin-Watson
1	.520 a	.270	.227	2.2247	1.798

c. Predictors: (Constant), Thigh Circumference (cm), Ethnicity, Injection Type, Age, Gender BMI

d. Dependent Variable: VAS Immediately After Local Sciatic

Table 9: Model Summary

Model		Sum of Squares	dF	Mean Square	F	Sig.
1	Regression	183.449	6	30.575	6.178	.000 b
	Residual	494.930	100	4.949		
	Total	678.379	106			

c. Dependent Variable: VAS Immediately After Local Sciatic

d. Predictors: (Constant), Thigh Circumference (cm), Ethnicity, Injection Type, Age, Gender BMI

Table 10: ANOVAa

		Unstandardized Coefficients		Standardized Coefficients				95% Confidence Interval for B	
Model		B	Std. Error	Beta	t	Sig.	Lower Bound	Upper Bound	
1	(Constant)	9.130	2.846		3.208	.002	3.484	14.777	
	Injection Type	-2.248	.433	-.446	-5.191	.000	-3.107	-1.389	
	Gender	.826	.457	.164	1.807	.074	-.081	1.179	
	Age	-.236	.142	-.147	-1.665	.099	-.517	-.040	
	Ethnicity	.005	.157	.003	.033	.973	-.307	.212	
	BMI	-.029	.087	-0.54	-.329	.743	-.201	.049	
	Thigh Circumference (cm)	-.028	.051	-.090	-.543	.588	-.130	.055	

b. Dependent Variable: VAS Immediately After Local Sciatic

Table 11: Coefficientsa

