### **1.7 Secondary Objectives**

- To evaluate the difference in pain from local anesthetic infiltration with J-tip needless injection compared to needle injection.
- To evaluate efficacy of femoral and/or sciatic nerve block after J-tip lidocaine injection compared to needle injected lidocaine post operatively by tracking pain levels to post operative day three.
- To assess patient and parent satisfaction with J-tip use.
- To assess changes in post operative pain medication amounts with J-tip use.
- To evaluate changes in post operative nausea and/or vomiting with J-tip use.
- To evaluate changes in post operative anti-nausea/anti-emetic medication use with J-tip use.
- To evaluate changes in time of PACU stay.

- To assess any differences in outcomes or pain after J-tip or needle injected lidocaine with respect to BMI, thigh circumference, gender, ethnicity or operative time in pain reporting measures, satisfaction or medication usage.

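### Both t-test conclusions reverse the direction of the J-Tip effect on infiltration pain, and five upper confidence limits in Table 11 are Table 7's values

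*Combined protocol and SAP*

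**What the plan says.** Pain from the local infiltration is a secondary outcome. Section 1.7 lists it first: "To evaluate the difference in pain from local anesthetic infiltration with J-tip needless injection compared to needle injection"; section 3.2 adds that it is measured by VAS.

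The Results report it in three ways:

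- **Descriptive Statistics.** "The mean VAS immediately after local femoral for J-Tip injections is 2.03 less than the mean VAS immediately after local femoral for Needle Injections". The sciatic text says the same with 2.228, and Table 1 gives the means behind both.
- **Two-Sample T Test.** The femoral conclusion is "The VAS Immediately After Local Femoral for J-Tip Injections exceeds the mean VAS Immediately After Local Femoral for Needle Injections" and the sciatic conclusion is "The VAS Immediately After Local Sciatic for J-Tip Injections exceeds the mean VAS Immediately After Local Sciatic for Needle Injections", each said to be statistically significant. Table 2 gives positive mean differences of 2.030 and 2.2281.
- **Ordinary Least Squares Regression.** The injection-type coefficients are -2.020 (Table 7, femoral) and -2.248 (Table 11, sciatic). The sciatic text reads "The beta explains that if a J-tip injection was given it would decrease the VAS immediately after local sciatic by approximately 2".

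The age row of Table 7 is "Age -.250 .105 -.193 -2.367 .020 -.459 -.040" and that of Table 11 is "Age -.236 .142 -.147 -1.665 .099 -.517 -.040". The last two entries in each are the 95% limits. The upper limit is the same in both, although the coefficient, standard error and lower limit differ.

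**The concern.** Taken alone, the two formal conclusions say that the J-Tip hurts significantly more than the needle. Anyone extracting results from the hypothesis-test section would record the wrong direction. The positive differences and intervals in Table 2 seem to support that reading, because neither the table nor its text says that the difference is needle minus J-Tip.

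The Table 11 problem is of a different kind. A regression confidence interval is centred on its coefficient, and five of the printed intervals are not. Four of the five covariates (gender, ethnicity, BMI, thigh circumference) are named in the last secondary objective of section 1.7. For the fifth, age, the interval and the p-value in the same row give opposite answers at the 5% level.

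**Working it through.** **1. Direction and Table 2, from Table 1**

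Inputs are N, mean and SD. Femoral: needle 54, 3.57, 2.133; J-Tip 57, 1.54, 1.524. Sciatic: needle 54, 4.500, 2.4553; J-Tip 57, 2.272, 2.1631. The difference is taken as needle minus J-Tip.

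- Femoral difference: 3.57 - 1.54 = +2.03.
  - Pooled variance: SE = 0.350, t = 2.03/0.350 = 5.79 on 109 df, 95% CI 1.335 to 2.725. Table 2 prints 5.792, 1.336 to 2.725.
  - Unequal variances: SE = sqrt(2.133²/54 + 1.524²/57) = 0.354, t = 5.742 on 95.52 df, CI 1.328 to 2.732. Table 2 prints 5.741, 95.525, 1.328 to 2.732.
- Sciatic difference: 4.500 - 2.272 = +2.228. Pooled SE = 0.4386, t = 5.079 on 109 df, CI 1.3586 to 3.0974. Table 2 prints 5.080, 1.3587 to 3.0974.

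Table 2 is therefore right, and its sign works only as needle minus J-Tip. A positive difference means that J-Tip is lower.

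The femoral sentence also reports t = 5.792 with 95.525 df and the interval 1.328 to 2.732. That t belongs to the equal-variance row; the df and interval belong to the unequal-variance row, where t is 5.741.

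**2. Table 11 upper limits**

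The residual df is 100 (Table 10), so t(.975, 100) = 1.984 and the upper limit is B + 1.984 × SE. The range comes from moving B and SE by ±.0005 for rounding.

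| Row | B | SE | Upper limit, computed (range) | Upper limit, Table 11 | Upper limit, Table 7 |
|---|---|---|---|---|---|
| Gender | .826 | .457 | 1.733 (1.731 to 1.734) | 1.179 | 1.179 |
| Age | -.236 | .142 | 0.046 (0.044 to 0.047) | -.040 | -.040 |
| Ethnicity | .005 | .157 | 0.316 (0.315 to 0.318) | .212 | .212 |
| BMI | -.029 | .087 | 0.144 (0.142 to 0.145) | .049 | .049 |
| Thigh circumference | -.028 | .051 | 0.073 (0.072 to 0.075) | .055 | .055 |

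No printed limit falls in its range. A second route, reflecting the printed lower limit about B (2B - lower), gives 1.733, 0.045, 0.317, 0.143 and 0.074.

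As a control, the same formula reproduces to within rounding all 14 limits in Table 7, all seven lower limits in Table 11, and Table 11's upper limits for the constant (14.776 against 14.777) and injection type (-1.389). Only these five cells fail.

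Printed against expected widths: gender 1.260 and 1.813, age .477 and .563, ethnicity .519 and .623, BMI .250 and .345, thigh .185 and .202. The shortfall runs from 1 - .185/.202 = about 8 to 9% (thigh) to 1 - 1.260/1.813 = about 31% (gender).

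For age, t = -1.665 on 100 df gives p = .099, as printed. That is consistent with an interval reaching +0.046 and not with one ending at -.040. The other four intervals include zero whichever upper limit is used.

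**3. Smaller discrepancies**

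- Adjusted R², sciatic: 1 - (1 - 183.449/678.379) × 106/100 = .2266. The text and Table 9 give .227; Table 8 prints .277.
- BMI standardized beta, sciatic, printed in "BMI -.029 .087 -0.54 -.329 .743 -.201 .049" as -0.54. Assuming the same 107 patients in both models, Table 7 implies SD(BMI) = (.186/.079) × sqrt(442.467/106) = 4.81. Then beta = -.029 × 4.81 / sqrt(678.379/106) = -.055. A displaced decimal point (-.054) fits this within rounding.

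**The case against.** The strongest reply is that no careful reader would be misled. The descriptive text before the t-tests and the regression text after them both give the right direction, and Table 1 and the hypotheses list needle before J-Tip, so the order of subtraction can be worked out. That is true, and it limits the harm, but a formal conclusion should not need its neighbours to correct it.

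On Table 11, the one interval that changes relative to zero is for age, which is not among the factors named in section 1.7. The text draws no conclusion from it, and the correct p-value stands in the same row. This also holds, so the error distorts precision more than inference.

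The adjusted R² and the BMI beta differ by one digit or a decimal point and could be machine-reading errors. For those two that caution is fair. It does not explain five consecutive cells that match another table exactly.

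Finally, section 7 plans exact and non-parametric tests, while the Results use t-tests. Correcting the sentences makes the reported t-tests read correctly; it does not show that the planned analysis was done.

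**Conclusion.** The concern holds. Two formal conclusions reverse the sign of a 2.03-point and a 2.23-point VAS difference that Table 1, Table 2 and both regressions show to favour the J-Tip. Five upper limits in Table 11 duplicate Table 7 and miss the values implied by Table 11's own estimates by 0.018 (thigh) to 0.554 (gender), against a rounding tolerance of about 0.002. Only the age interval changes its relation to zero.

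These are reporting errors. The treatment estimates, their intervals and their p-values are sound, and the non-significant comparisons of pain at the block itself, listed at the start of the regression section, are not touched. The recomputation assumes only that the printed coefficients and standard errors are right, which the matching lower limits and p-values support. The BMI beta figure also assumes the same patients in both models. The corrections should be made, because these sentences and intervals are what the document reports as its results.

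**What to change.** 1. Replace the femoral conclusion with: *Mean VAS immediately after local femoral was lower with J-Tip than with needle (needle minus J-Tip 2.030; t(95.525) = 5.741, p < .01, 95% CI 1.328 to 2.732).* This also removes the mixed t and df.
2. Replace the sciatic conclusion with: *Mean VAS immediately after local sciatic was lower with J-Tip than with needle (needle minus J-Tip 2.2281; t(109) = 5.080, p < .01, 95% CI 1.3587 to 3.0974).*
3. Label the difference in Table 2 as needle minus J-Tip.
4. Re-export Table 11 from the model output. The limits computed above should not be typed in, because they rest on rounded inputs. Check the BMI standardized beta against the same export.
5. Correct the adjusted R² in Table 8 to .227.

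The cost is two sentences, one label, one re-exported table and one cell. No new data or re-analysis is needed.
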